3.1. Description of the Study Population

Patients are eligible to enroll if they satisfy all of the 5 inclusion conditions and patients are excluded if they satisfy any of the 11 exclusion conditions as outlined in Table 1 below.

Table 1. Inclusion and Exclusion Criteria.

Inclusion Criteria:
(1) Survival of an episode of suicidal self-directed violence (including suicide attempts and interrupted attempts) that occurred within three months of initial consent to the study , or they were admitted to a mental health inpatient unit specifically to prevent suicide within three months of initial consent to the study
(2) Diagnosis of Bipolar I Disorder, Bioplar II Disorder, or current or recurrent Major Depressive Disorder. Meeting the diagnosis for a current Major Depressive Disorder requires the presence or history of a Major Depressive Epidosde
(3) Concurrence from the patient's mental health provider and the provider responsible for the pateint's general medical care about inclusion/exclusion criteria, and confirmation of the providers' willingness to work with the research team in managing the patient throughout the study
(4) Able to provide informed consent
(5) Patient identifies one or more contacts and gives permission for the clinical providers and/or the research team to contact them if the patient cannot be reached.

Exclusion Criteria:
(1) Schizophrenia
(2) A history of psychotic symptoms in the absence of prominent mood symptoms attributable to Major Depressive or Manic Episodes, delirium, or substance use/withdrawal
(3) Six or more previous lifetime suicide attempts
(4) Enrollment in another randomized interventional clinical trial
(5) Lack of decision-making capacity to evaluate the risks versus the benefits of participation as determined by UBACC score <14
(6) Cognitive impairment defined by a score >10 on the OMC
(7) Current or recurrent (within the past 6 months) use of lithium, or a history of significant adverse effects of lithium
(8) Concurrent medications: a.Diuretics b.Angiotensin Converting Enzyme Inhibitors (ACE Inhibitors) c.Angiotensin II Receptor Antagonists d.Haloperidol e.Clozapine
(9) Unstable medical conditions or specific medical comorbidity: 
• Congestive heart failure by Framingham criteria (See form S12 for worksheet)• Estimated GFR < 60 mL/min/1.73m²

QTc \geq 450ms for men and \geq 460ms for women
(10) Active substance abuse: 
 • Active alcohol or opiate dependence requiring medically supervised withdrawal and stabilization • Active cocaine, methamphetamine, other stimulant, hallucinogen, or cannabis abuse requiring stabilization
(11) Any possibility of being pregnant, not on appropriate birth control, lactation and breastfeeding

3.2. Description of the Intervention Strategy

Eligible patients who consent to participate will be randomized to receive Lithium or placebo. Initial dosage will be 600 mg /day of lithium (or matching placebo), to be titrated to achieve serum lithium level of 0.6 to 0.8 meq/liter. Mock serum lithium level for placebo patients will be calculated using Therapeutic Drug Monitoring method (Yukawa, 1993) based on age, weight, serum creatinine level, adherence, and side-effects. Titration visits will occur at intervals of 5-7 days over 3 months, with maximum allowed dosage not to exceed 1500mg.

Once the target serum lithium level has been reached the patient will be on steady state maintenance phase for the rest of the study with active participation and intervention terminating at 12 months after randomization.

3.3. Definition of Intention to Treat Primary Analytic Sample

All consented and randomized subjects will be accounted for and included in the primary intention to treat (ITT) analytic cohort. Those who revoked HIPAA authorization will be included in the analysis from randomization date to date of HIPAA revocation.

An analytic datafile consisting of only the “ITT” subjects as defined above will be created and maintained throughout the study. This file will be called the “CSP590_ITT” file.

3.4. Definition of per-Protocol sample

Adherence to allocated intervention will be ascertained for randomized subjects for identification of “per-Protocol” sub-group. Adherence will be determined by pill count for both lithium and placebo groups and additionally, by serum lithium level for the lithium group. These two methods are described below. Those in the lithium intervention group who are adherent to the protocol based on either of the two methods will be considered as adherent. All study subjects, who are adherent to the protocol, will be included in the “per-Protocol” analytic sub-sample.

Method 1: Based on pill count from Form T03 Study Drug Adherence Form data.

Percent adherence for each prescribed dosage will be computed using the following algorithm:

$$\% \text{ adherence} = (\text{Total \#tablets taken} / \text{Total \#tablets prescribed}) * 100\%$$

These percent adherences for each prescribed dosage will be averaged for each patient and those with $\geq 80\%$ overall adherence during the steady state follow up period will be considered adherent to the protocol.

Method 2: Based on target serum lithium level

Study participants in the lithium augmentation group who reach the target serum lithium level of 0.6-0.8 meq/liter during the titration period and maintain within target ± 0.1 meq/liter (i.e., 0.5-0.9 meq/liter) during the entire steady state follow up period will be considered adherent to the protocol.

4. Primary Analysis

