- 1) Calculate a plasma level for the current dose using the method of Abou-Auda (2008).

- 2) Adjust the plasma upwards if there are reports of side effects, and downward, if there are reports of non-adherence; these adjustments are intended to ensure that the simulated plasma levels appear plausible and realistic in light of the patient's clinical status.
- 3) Multiply the adjusted value by a random factor. This is necessary to ensure that there is a realistic degree of week to week variability for simulated plasma levels and that the reported values cannot signal the Research Team at the study site about whether the plasma levels are real or simulated.

During the course of the study, the study biostatistician will periodically compare the distributions of real and simulated plasmas levels to ensure that there are no significant differences. Should there be trends suggesting they are diverging, the biostatistician will work with the MAVERIC data coordinating center to revise the parameters for calculating simulated measures.

All participants will have flags in their VA electronic medical records in accordance with local policy. This study falls under the 1200.05 2012 version, however, we recommend that the flags state that the participants are enrolled in a research study and any medication changes or drug level testing be done only after consulting the Site Physician. The amount of information provided within the flags may vary by site according to local policies and procedures.

The processes for dispensing medication from a VA pharmacy or by mail will be developed for each patient, depending upon whether patients are inpatients (at the start of the study) or outpatients, and whether or not they have convenient access to a VA facility. Medications will be dispensed in blister cards containing medication for two weeks. Some participants may be dispensed one week of medication at a time if the investigator determines this is more appropriate for the safety of the participant. Participants will be asked to return unused blister cards at the next study visit to perform tablet counts to assess adherence.

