4.5. Sensitivity Analysis

The primary efficacy analysis will be repeated under 3 different scenarios as follows.

- (1) Randomization was stratified on two factors: (1) Bipolar or Major Depressive Disorder diagnosis, and (2) prior history of suicide attempt. Cox Regression Model as described in section 4.3 will be refitted with the inclusion of diagnosis variable and suicide history variable in the model.
- (2) Primary efficacy analysis will be repeated on the “per-Protocol” sample with adherence as defined in section 3.4 to evaluate efficacy among those adherent to the protocol.
- (3) Primary efficacy analysis will be repeated on the modified ITT analytic cohort that excludes all randomized subjects who terminated prior to the first titration visit.

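### The per-protocol set is selected by different adherence rules in the two arms, so its hazard ratio can depart from 1 with no drug effect

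*SAP*

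**What the plan says.** SAP 3.4 sets out the measures by arm: "Adherence will be determined by pill count for both lithium and placebo groups and additionally, by serum lithium level for the lithium group".

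- **Method 1, both arms.** Tablets taken are divided by tablets prescribed (Form T03), averaged over the prescribed dosages. A patient with at least 80% "overall adherence during the steady state follow up period will be considered adherent to the protocol".
- **Method 2, lithium only.** It applies to patients "who reach the target serum lithium level of 0.6-0.8 meq/liter during the titration period" whose level then stays within 0.5-0.9 meq/L throughout steady state.
- **Combination.** "Those in the lithium intervention group who are adherent to the protocol based on either of the two methods will be considered as adherent".

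SAP 4.5(2) repeats the primary efficacy analysis on this sample, "to evaluate efficacy among those adherent to the protocol".

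Placebo patients do have levels on file. SAP 3.2 states: "Mock serum lithium level for placebo patients will be calculated using Therapeutic Drug Monitoring method". These mock levels play no part in the adherence rule.

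**The concern.** The either-method rule can add lithium patients to the set but never remove one, and placebo has no matching route. A lithium patient who fails the pill count may stay in on level, while a placebo patient with the same pill count is out. If pill-count failure is related to the risk of a suicidal event, the arms then differ in baseline risk because of the rule.

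This matters because the analysis is meant to show efficacy in adherent patients, and the protocol expects non-adherence to dilute the effect (Section VII, Estimated Effect of the Intervention). Readers may turn to it if the primary result is null or borderline. SAP 4.4, 4.5 and 4.6 contain no common-rule version, weighting or adjustment that would offset the difference.

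**Working it through.** The plan gives no size, event count or power for the per-protocol sample, so there is no stated figure to reproduce. The check is one of logic, followed by an illustration.

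**Logic.** Let p be the share passing the pill count, taken as equal in both arms, and s the share of lithium pill-count failures who pass on level. The share admitted is p on placebo and p + (1 - p)s on lithium. The lithium share is larger whenever s > 0.

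**Illustration 1: hazards.** Assume no drug effect. Let r be the hazard of level-only entrants relative to pill-count passers. Averaging hazards within the lithium set gives

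HR = [p + (1 - p)·s·r] / [p + (1 - p)·s].

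With p = 0.5 this becomes (0.5 + 0.5·s·r)/(0.5 + 0.5·s). The values of p, s and r are assumptions, not document values.

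| s | Lithium admitted | Placebo admitted | HR, r = 2 | HR, r = 0.5 |
|---|---|---|---|---|
| 0.1 | 55% | 50% | 0.60/0.55 = 1.09 | 0.525/0.55 = 0.95 |
| 0.2 | 60% | 50% | 0.70/0.60 = 1.17 | 0.55/0.60 = 0.92 |
| 0.3 | 65% | 50% | 0.80/0.65 = 1.23 | 0.575/0.65 = 0.88 |

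With s = 0 or r = 1 the ratio is 1.00.

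**Illustration 2: one-year risks over a wider grid.** Take the planned 15% placebo event rate (SAP 4.3) as the overall risk in both arms. Vary p from 0.4 to 0.8, matching the 20-60% range of full or partial non-adherence cited in Protocol Section VII (Non-Adherence to Study Protocol). Let k be the risk of pill-count failures relative to passers, and give level-only entrants the failures' risk. The values of s and k are again assumptions.

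Worked case with p = 0.60, s = 0.25, k = 2:
- Passers' risk: 0.15/(0.60 + 0.40 × 2) = 0.1071. Failures' risk: 0.2143.
- Admitted: 0.60 + 0.40 × 0.25 = 70% on lithium, against 60% on placebo.
- Lithium set risk: (0.60 × 0.1071 + 0.10 × 0.2143)/0.70 = 0.1224.
- HR = ln(1 - 0.1224)/ln(1 - 0.1071) = 1.15.

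At the same p and s, the HR is 1.08 for k = 1.5, 1.00 for k = 1 and 0.95 for k = 0.67. Over p = 0.4-0.8, s = 0.1-0.5 and k = 0.67-2 it runs from 0.85 to 1.46.

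**Effect of a common rule.** Pill count alone in both arms is the case s = 0. Both arms then admit p, and the HR is 1.00 in every scenario. This holds by construction, because the model takes pill-count passers to be comparable between arms.

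**The case against.** The case for the rule is that serum level measures exposure more directly than returned tablets, so it rescues lithium patients whose pill count is wrong. That is true, but the rescue works in one arm only. A placebo patient with an equally wrong count is excluded.

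Method 2 is also strict. The patient must reach target in titration and stay in the wider band for the whole of steady state, so few may enter by level alone. This objection stands as to size, though the documents do not settle it. Levels are drawn monthly to month 6 and then quarterly for most patients (Protocol XIII, Study medications). The SAP does not say how absent levels count.

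Four stronger readings are tempting, and the documents do not support them.

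- *The hazard ratio is biased, and in lithium's favour.* The illustrative values fall on both sides of 1. Nothing in the documents fixes the number or the risk of level-only entrants.
- *Much of the robustness case rests on this analysis.* SAP 4.5 lists three analyses, but SAP 4.6 adds a Bayesian pattern-mixture sensitivity analysis, and SAP 4.4 refits the Cox model with covariates and with a site frailty. The minimum content of the final report (SAP 11) does not name the per-protocol analysis.
- *Judging adherence only in steady state adds a further bias between arms.* Survival time does start at randomisation. However, SAP 3.4 does not say how patients without steady-state data are classified, and the pill-count window is the same in both arms.
- *Mock levels could give placebo patients a matching second route.* Protocol XIII (Titrating study medication) tells the coordinating center to "Adjust the plasma upwards if there are reports of side effects, and downward, if there are reports of non-adherence". They are therefore not an independent measure of exposure.

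**Conclusion.** The asymmetry is explicit, and no other part of the SAP offsets it. The per-protocol comparison can show a difference between arms with no drug effect, unless nobody enters by level alone or pill-count failure is unrelated to risk. At p = 0.5 and s = 0.1-0.3 the null hazard ratio is 1.09-1.23 or 0.95-0.88, depending on whether level-only entrants have twice or half the hazard of passers. These figures show what the rule could do and do not estimate what it will do. The true size could be close to nil if Method 2 admits few patients.

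The point is confined to SAP 4.5(2). The primary intention-to-treat log-rank test, its type I error and the sample size are untouched. It should be corrected because the defect is clear and cheap to remove.

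**What to change.** In SAP 3.4, define the per-protocol set in both arms by the same rule: at least 80% pill-count adherence from Form T03. Remove serum level as a route into the set, and report it only descriptively within the lithium arm.

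This is a change of wording and needs no new data. The cost is a smaller lithium set, reduced by whatever share qualified by level alone. At p = 0.5 that is 0.05/0.55 = 9% for s = 0.1 and 0.15/0.65 = 23% for s = 0.3. Errors in the pill count remain, but the same rule then applies to both arms.

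The change does not remove the post-randomisation selection present in any per-protocol analysis. Starting the per-protocol clock at steady state is not a sound addition. Entry to steady state varies by patient, and some never reach the target level (Protocol XIII, Titrating study medication). Adherence averaged over later follow-up would also still condition on the future.

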Lithium will be provided as extended-release lithium carbonate (or placebo) in 300 mg tablets. Subjects will be started on 600 mg/day (300 mg bid), unless there are clinical indications for starting at a lower dose (300 mg/day). Lithium (or placebo) plasma levels will be determined (by send-out central lab testing) after each dose adjustment (see section XIV, Titration Visits, for more detail) until steady state at target plasma levels between 0.6 and 0.8 mEq/L is achieved. Steady state is defined as a serum lithium level between 0.6 and 0.8 mEq/L, over 2 consecutive visits, at the same dose, and with the second level the same or 0.1 mEq/L lower than the first level. The target range will be operationalized by providing guidance to Site Physicians that they should stop titrating the dose upwards if proportional increases in plasma levels would exceed 0.8 mEq/L, that is, if the steady state plasma level on a dose of 300 mg/day exceeds 0.40 mEq/L or the level of a dose of 600mg/day exceeds 0.53 mEq/L. After steady state levels within the target range are achieved, the frequency of plasma level determinations will be decreased to monthly until the end of six month's participation, and then quarterly unless they are on an ACE inhibitor or a diuretic, in which case monthly monitoring will continue; they will be done more frequently when medically indicated in either the lithium or the placebo group.

The target plasma levels are within the range considered effective for other lithium indications. The 2010 VA-DoD Clinical Practice Guideline for Bipolar Disorder recommends target levels of 0.6-1.0 mEq/L for maintenance treatment; the 2009 VA-DoD Clinical Practice Guideline for Major Depressive Disorder recommends 0.5-1.0 mEq/L for the augmentation of antidepressant responses; and the 2002 American Psychiatric Association Guideline on Bipolar Disorder recommends 0.5-1.2 mEq/L. A 1998 observational study by Tondo et al. found an 85-90% reduction in suicide risk for patients on lithium with average plasma levels of 0.624 ± 0.134 mEq/L. Based on these data, target plasma levels for the Lauterbach study (2008) were 0.6-0.8 mEq/L, similar to those proposed for this study.

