For added safety, the site physician has the capacity to hold study medication for up to three days or decrease the dose as the clinical circumstances warrant. When determining the initial dose of study medication; if the site physician has concerns that factors such as aging, potential drug-drug interactions, or potential drug-disease interactions would decrease the tolerability of an initial dose of 600 mg of study medication, he or she could reduce the starting dose to 300 mg/day for the first interval.

During the course of the study, there may be unanticipated changes in the patient's medical condition, side effects or adverse reactions to study medication, new prescriptions of medications with potential drug-drug interactions, or other events associated with volume depletion or dehydration that could lead to adverse events through increased the serum level or increased tissue sensitivity. If any of these occur, the site physician may decrease the dose of study medication.

Whenever the site physician holds study medication or prescribes a reduced dose for reasons of safety, he or she will document the reason, and the duration of the "hold" or the actual dose prescribed. Also, at these times, the site physician will monitor the patient closely, e.g., through increased contact by telephone. Depending on the patient's clinical condition, further dose decreases may be necessary; decreases down to 300 mg/day are allowed by the protocol. If the patient is stable, the reduced dose will be maintained for approximately 5-7 days at which time another lithium level will be obtained and used to guide further dose adjustments, as appropriate.

When each patient is entered, the Research Team will forward information on physiological parameters including age, sex, height, weight, medications, medical conditions, and creatinine to the MAVERIC data coordinating center to allow estimations of the lithium clearance using empirical algorithms (e.g., Abou-Auda et al., 2008). At the time that blood levels are determined, the Research Team at the study site will provide the MAVERIC data coordinating center with updated information on laboratory parameters, information about changes in the patient's medications and medical status, and reports from the patient on adherence for study medications and side effects. To calculate the simulated lithium level, the MAVERIC data coordinating center will:

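### SAP 3.4 averages pill-count adherence over dosages with no weights and no cap, so a short reduced-dose spell can misclassify participants for the per-protocol analysis

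*SAP*

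**What the plan says.** SAP 3.4 builds the per-protocol sample from adherence. Method 1 uses pill counts from Form T03 and applies to both arms: "Percent adherence for each prescribed dosage will be computed using the following algorithm", namely total "tablets taken" over total prescribed, times 100. Then "These percent adherences for each prescribed dosage will be averaged for each patient", and those with at least 80% "overall adherence during the steady state follow up period will be considered adherent to the protocol". Neither document adds a weight or a maximum.

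SAP 3.2 uses the word dosage for a dose level, for instance "with maximum allowed dosage not to exceed 1500mg". Protocol XIII states that "Lithium will be provided as extended-release lithium carbonate (or placebo) in 300 mg tablets", so different dose levels mean different tablet counts per day.

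Protocol XIII also expects doses to change after titration. Under the titration heading, "the site physician has the capacity to hold study medication for up to three days or decrease the dose as the clinical circumstances warrant". A stable participant then stays on a reduced dose for roughly 5 to 7 days before the next lithium level. Under ongoing dose adjustments, the dose may be changed temporarily or from then on.

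The resulting sample is used in SAP 4.5, sensitivity analysis (2).

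**The concern.** A simple mean of ratios equals the overall proportion of tablets taken only when the ratios are equal or rest on equal denominators. Here the denominators can differ by a factor of more than 60: 900 tablets on a main dose against 14 in a week on a lower one. The small denominator gives the least stable percentage, yet it receives the same weight. Without a limit at 100%, tablets taken in excess during one dosage can also offset tablets missed in another.

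At stake is whether sensitivity analysis 4.5(2) describes the participants it is meant to describe. A participant who missed a quarter of the tablets can enter the adherent set, and one who took nearly nine in ten can be left out.

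**Working it through.** The SAP states no adherence figure that could be reproduced, so the check applies its rule to example participants.

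**Inputs from the documents**
- Threshold 80%, steady-state period (SAP 3.4).
- 300 mg tablets, so 900 mg/day is 3 tablets and 600 mg/day is 2 (Protocol XIII).
- Reduced-dose spell of about 5 to 7 days (Protocol XIII); 7 is used.
- Steady-state visits from about month 2 to month 12 (Protocol XIII, Table 6), so about 10 months.

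**Assumptions not in the documents**
- 300 days at 3 tablets/day (900 tablets) and 7 days at 2 tablets/day (14 tablets).
- The adherence level in each example.

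The short spell is 7/307 = 2.3% of the days and 14/914 = 1.5% of the tablets, but one half of a two-dosage average.

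**Dosage read as dose level.** Rule = (main % + short %)/2. Pooled = total taken / total prescribed.
- Example A: main 75%, short 100%. Rule (75 + 100)/2 = 87.5%, adherent. Pooled (675 + 14)/914 = 689/914 = 75.4%, not adherent. Shift 12.1 points.
- Example B: main 90%, short 6 of 14 tablets = 42.9%. Rule (90 + 42.9)/2 = 66.4%, not adherent. Pooled (810 + 6)/914 = 816/914 = 89.3%, adherent. Shift 22.9 points.
- In general the rule is passed when main % ≥ 160 − short %. With the short spell at 100%, a main-dose figure of 60% passes. With it at 50%, the main dose would need 110%, so a participant who took every main-dose tablet fails.

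The result does not depend on exactly 7 days. With 14 days the rule gives the same averages, and pooling gives 703/928 = 75.8% (A) and 822/928 = 88.6% (B).

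**Unit read as a visit or dispensing record** (ten monthly records plus one short record).
- Example A: (10 × 75 + 100)/11 = 77.3%, not adherent; 1.9 points from pooled.
- Example B: (10 × 90 + 42.9)/11 = 85.7%, adherent; 3.6 points from pooled.
- The main-dose figure needed is (880 − short %)/10: 78% with the short record at 100%, 83% with it at 50%. Only participants near 80% can change class.

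**No limit at 100%.** Suppose the main dose is at 50% and the participant keeps taking 3 tablets/day for 7 days after a cut to 2, so the short spell is 21/14 = 150%. The rule gives (50 + 150)/2 = 100%. Capping the short spell gives 75%. Pooled is (450 + 21)/914 = 51.5%, or 464/914 = 50.8% with the cap.

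**Holds.** The SAP does not say whether held tablets count as prescribed. If they do, a fully compliant participant with a 3-day hold inside the 7-day spell scores 8/14 = 57.1% there, and (100 + 57.1)/2 = 78.6% overall: not adherent, for following the physician's instruction.

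**One dose throughout steady state.** At 78%, both the rule and pooling give 78%.

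**The case against.** The strongest reply is that the SAP says only that the percentages are averaged, and the simple mean over dose levels is a reading. The data come from Form T03, which Protocol Table 6 schedules at every treatment visit after baseline, and the form is not available here. If each record is the unit, both examples are classified correctly. This stands as a limit on size. It does not settle the matter, because SAP 3.2 uses dosage for dose level and the same participants change class with the reading.

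Several stronger conclusions are tempting but not supported:
- *The errors fall mainly on lithium.* No dose-change rate is given for either arm. Placebo doses are also adjusted, on simulated levels that are raised when side effects are reported (Protocol XIII). The examples err in both directions, so no direction of bias follows. A lithium participant wrongly failed on pill count may still qualify on serum level (Method 2) and a placebo participant cannot. That asymmetry comes from the either-method rule.
- *A corrected rule would give a comparison of people who took at least 80% of their drug.* It would not, since a lithium participant can enter on serum level alone.
- *Overdoses would inflate the figure materially.* Protocol VIII cites about 1% from two earlier trials, and nothing shows how an overdose would be entered on Form T03. Cards hold limited supplies, so counted excess needs carried-over tablets or a dose cut while a card is in use. This route is minor.

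It is also fair that steady state requires two consecutive visits at one dose, so most titration changes lie outside the period. Pooling is likewise not the only defensible summary, because it gives higher-dose periods more weight.

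**Conclusion.** The point holds in a limited form. Read plainly, Method 1 can misclassify participants whose dose changed during steady state, in either direction, by about 12 to 23 points in the examples. If the unit is a visit or dispensing record, the shift is about 2 to 4 points. The examples rest on assumed durations and adherence levels, and on taking the average as unweighted.

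The averaging does not affect anyone who stays on one steady-state dose. The documents do not give the share of participants with dose changes, so neither the number misclassified nor any imbalance between arms can be computed. The consequence is confined to one of the three sensitivity analyses; the primary log-rank test, its type I error and the sample size are untouched. It is still worth correcting, because following the rule as written can produce a wrong per-protocol set and a better rule is available at almost no cost.

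**What to change.** Before unblinding, replace the averaging step in SAP 3.4, Method 1, with one ratio per participant:
- Total tablets taken divided by total tablets prescribed over the whole steady-state period, all dose levels together. A day-weighted mean is an acceptable alternative: it gives (300 × 75 + 7 × 100)/307 = 75.6% in Example A and (300 × 90 + 7 × 42.9)/307 = 88.9% in Example B, the same classifications as pooling.
- Leave documented investigator-hold days out of the denominator. Protocol XIII already requires the reason and duration of a hold to be recorded.
- Cap tablets taken at tablets prescribed within each dispensing interval, and report intervals above 100% separately as over-use.

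The cost is a short SAP amendment and a small programming change on Form T03 data already being collected. No clinical procedure changes.
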